10.4.4. Reporting Adverse Events Leading to Withdrawal from the Study

All AEs that lead to a subject's withdrawal from the study must be reported to the sponsor's medical monitor within 30 days.

Regeneron Pharmaceuticals, Inc.

CONFIDENTIAL

Page 89 of 118

Refer to the study reference manual for the procedures to be followed.

10.4.5. Abnormal Laboratory or Vital Signs Results

Abnormal laboratory or vital signs will be graded according to the FDA September 2007. The criteria for determining whether an abnormal objective test finding should be reported as an AE include:

- the test result is associated with accompanying symptoms, and/or
- the test result requires additional diagnostic testing or medical/surgical intervention, and/or
- the test result leads to a change in dosing (outside of protocol-stipulated dose adjustments), discontinuation from the study, significant additional concomitant drug treatment, or other therapy

Contact the medical monitor in the event the investigator feels that an abnormal test finding should be reported as an AE, although it does not meet any of the above criteria.

Repeating an abnormal test, in the absence of any of the above conditions, does not constitute an AE. Any abnormal test result that is determined to be an error does not require reporting as an AE.

Please refer to FDA Guidance for Industry, Toxicity Grading Scale for Healthy Adult and Adolescent Volunteers Enrolled in Preventive Vaccine Clinical Trials for reporting severity of laboratory abnormalities:

(https://www.fda.gov/downloads/BiologicsBloodVaccines/GuidanceComplianceRegulatoryInfor mation/Guidances/Vaccines/ucm091977.pdf)

10.4.6. Follow-Up

Adverse event information will be collected until the subject's last study visit.

Serious adverse event information will be collected until the event is considered chronic and/or stable.

10.5. Evaluation of Severity and Causality

10.5.1. Evaluation of Severity

The severity grading of allergic reactions will be according to the definitions developed the CoFAR group (Appendix 2) and the severity of anaphylactic reactions will be graded according to the EAACI system for grading the severity of anaphylactic reactions (Appendix 3).

The severity of other AEs will be graded according to the following scale:

- **Mild:** Does not interfere in a significant manner with the subject normal functioning level. It may be an annoyance. Prescription drugs are not ordinarily needed for relief of symptoms but may be given because of personality of the subject.
- **Moderate:** Produces some impairment of functioning but is not hazardous to health. It is uncomfortable or an embarrassment. Treatment for symptom may be needed.

Regeneron Pharmaceuticals, Inc.

CONFIDENTIAL

Page 90 of 118

• Severe: Produces significant impairment of functioning or incapacitation and is a definite hazard to the subject's health. Treatment for symptom may be given and/or subject hospitalized.

If a laboratory value is considered an AE, its severity should be based on the degree of physiological impairment the value indicates.

Injection Site Reactions

The severity of injection site reactions will be graded according to the following scale (semi-colon indicates "or" within description of grade):

- **Mild**: Pain that does not interfere with activity; mild discomfort to touch; <5 cm of erythema or induration that does not interfere with activity
- **Moderate**: Pain that requires repeated use of non-narcotic pain reliever >24 hours or interferes with activity; discomfort with movement; 5.1 cm to 10 cm erythema or induration or induration that interferes with activity
- Severe: Pain that requires any use of narcotic pain reliever or that prevents daily activity; significant discomfort at rest; >10 cm erythema or induration; prevents daily activity; requires emergency room visit or hospitalization; necrosis; or exfoliative dermatitis

10.5.2. Evaluation of Causality

Relationship of Adverse Events to Study Drug:

The relationship of AEs to study drug will be assessed by the blinded investigator and will be a clinical decision based on all available information. The following question will be addressed:

Is there a reasonable possibility that the AE may have been caused by the study drug?

The possible answers are:

- **Not Related:** There is no reasonable possibility that the event may have been caused by the study drug
- **Related:** There is a reasonable possibility that the event may have been caused by the study drug

The investigator should justify the causality assessment of each SAE.

A list of factors to consider when assessing the relationship of AEs to study drug is provided below. Please note that this list is not exhaustive.

Is there a reasonable possibility that the event may have been caused by the study drug?

No:

- due to external causes such as environmental factors or other treatment(s) being administered
- due to subject's disease state or clinical condition

Regeneron Pharmaceuticals, Inc.

CONFIDENTIAL

- do not follow a reasonable temporal sequence following the time of administration of the dose of study drug
- do not reappear or worsen when dosing with study drug is resumed
- are not a suspected response to the study drug based upon preclinical data or prior clinical data

Yes:

- could not be explained by environmental factors or other treatment(s) being administered
- could not be explained by subject's disease state or clinical condition
- follow a reasonable temporal sequence following the time of administration of the dose of study drug
- resolve or improve after discontinuation of study drug
- reappear or worsen when dosing with study drug
- are known or suspected to be a response to the study drug based upon preclinical data or prior clinical data

Relationship of Adverse Events to Background Treatment:

The relationship of AEs to background treatment, etc. will be assessed by the ("blinded") investigator and will be a clinical decision based on all available information. The following question will be addressed:

Is there a reasonable possibility that the AE may have been caused by the background treatment, etc.?

The possible answers are:

Not Related: There is no reasonable possibility that the event may have been caused by the background treatment, etc.

Related: There is a reasonable possibility that the event may have been caused by the background treatment, etc.

The sponsor will request information to justify the causality assessment of SAEs, as needed.

A list of factors to consider in assessing the relationship of AEs to background treatment, etc. is provided below. Please note that this list is not exhaustive.

Is there a reasonable possibility that the event may have been caused by the background treatment?

No:

- due to subject's disease state or clinical condition
- do not follow a reasonable temporal sequence following the background treatment
- do not reappear or worsen when background treatment is resumed

Regeneron Pharmaceuticals, Inc.

CONFIDENTIAL

Page 92 of 118

• are not a suspected response to the background treatment based upon preclinical data or prior clinical data

Yes:

- could not be explained by environmental factors or other treatment(s) being administered
- could not be explained by subject's disease state or clinical condition
- follow a reasonable temporal sequence following the background treatment
- resolve or improve after discontinuation of background treatment
- reappear or worsen when background treatment is resumed
- are known or suspected to be a response to the background treatment based upon preclinical data or prior clinical data

10.6. Safety Monitoring

The investigator will monitor the safety of study subject at his/her site(s) as per the requirements of this protocol and consistent with current Good Clinical Practice (GCP). Any questions or concerns should be discussed with the sponsor in a timely fashion. The sponsor will monitor the safety data from across all study sites. The medical monitor will have primary responsibility for the emerging safety profile of the compound, but will be supported by other departments (eg, Pharmacovigilance and Risk Management; Biostatistics and Data Management). Safety monitoring will be performed on an ongoing basis (eg, individual review of SAEs) and on a periodic cumulative aggregate basis.

10.7. Investigator Alert Notification

Regeneron (or designee) will inform all investigators participating in this clinical trial, as well as in any other clinical trial using the same investigational drug, of any SAE that meets the relevant requirements for expedited reporting (an AE that is serious, unexpected based on the Investigator's Brochure or this protocol, and has a reasonable suspected causal relationship to the study drug).

11. STATISTICAL PLAN

This section provides the basis for the statistical analysis plan (SAP) for the study. The SAP may be revised during the study to accommodate amendments to the clinical study protocol and to make changes to adapt to unexpected issues in study execution and data that may affect the planned analyses. The final SAP will be issued before the database is locked.

Analysis variables are listed in Section 5.

Handling of missing data or delayed procedures due to COVID-19, and any additional analyses required to investigate the impact of COVID-19 to understand estimated treatment effect and safety, will be detailed in the SAP.

11.1. Statistical Hypothesis

The primary efficacy endpoint is the proportion of subjects who achieve a cumulative dose of 2044 mg peanut protein during a post up-dosing DBPCFC at visit 16. The comparison between the dupilumab plus AR101 arm and the placebo plus AR101 arm will be made.

Let p_D (and p_P) be the true proportion of subjects who achieve a cumulative dose of 2044 mg of peanut protein during a post up-dosing DBPCFC at visit 16 in the treatment arms of dupilumab plus AR101 and placebo plus AR101, respectively. The following hypothesis for the superiority testing will be tested at the 5% 2-sided significance level:

 H_0 : $p_D = p_P$, ie, the proportion of subjects who achieve a cumulative dose of 2044 mg peanut protein during a post up-dosing DBPCFC at visit 16 is the same between dupilumab plus AR101 arm and the placebo plus AR101 arm

against the alternative

 $H_a: p_D \neq p_P$, ie, the proportion of subjects who achieve a cumulative dose of 2044 mg peanut protein during a post up-dosing DBPCFC at visit 16 are different between the dupilumab plus AR101 arm and the placebo plus AR101 arm

11.2. Justification of Sample Size

It is assumed that the proportion of subjects who achieve a cumulative dose of 2044 mg of peanut protein during a post up-dosing DBPCFC at visit 16 in the placebo plus AR101 arm will be 40%, based on an Aimmune presentation at the 2018 American Academy of Allergy, Asthma & Immunology–World Allergy Organization Joint Congress; with the proportion of subjects in the dupilumab plus AR101 arm assumed to be 65%, which is considered to be clinical meaningful benefit by adding on dupilumab treatment. A sample size of approximately 156 subjects (104 in dupilumab plus AR101 and 52 in placebo plus AR101) will have 80% power to detect the treatment difference of 25% between placebo plus AR101 and dupilumab plus AR101 at the 2-sided 5% significance level (the minimum significant difference is approximately 17.8%). The sample size calculations were done by Fisher exact test using nQuery (7.0).

Approximately 122 subjects who undergo the post up-dosing DBPCFC at week 28 (visit 16 with a window of -7/+30 days) or discontinue from study prior to week 28 (visit 16 with a window of -7/+30 days) will be included in the primary efficacy analysis. These subjects receive AR101 dose escalation per the original protocol's 24-week up-dosing schedule. The minimum significant

difference with approximately 122 subjects is approximately 20.7% between placebo plus AR101 and dupilumab plus AR101 assuming the placebo plus AR101 treatment effect is 40% at the 2-sided Fisher exact test with 5% significance level.

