Statistical Plan	Sample Size It is assumed that the proportion of subjects who achieve a cumulative dose of 2044 mg of peanut protein during a post up-dosing DBPCFC at visit 16 in the placebo plus AR101 arm will be 40%, based on the Aimmune presentation at the 2018 American Academy of Allergy, Asthma & Immunology–World Allergy Organization Joint Congress with the proportion of subjects in the dupilumab plus AR101 arm assumed to be 65%, which is considered to be clinical meaningful benefit by adding on dupilumab treatment. A sample size of approximately 156 subjects (104 in dupilumab plus AR101 and 52 in placebo plus AR101) will have 80% power to detect a treatment difference of 25% between placebo plus AR101 and dupilumab plus AR101 at the 2-sided Fisher exact test with 5% significance level (the minimum significant difference is approximately 17.8%).	
	dupilumab treatment. A sample size of approximately 156 subjects (104 in dupilumab plus AR101 and 52 in placebo plus AR101) will have 80% power to detect a treatment difference of 25% between placebo plus AR101 and dupilumab plus AR101 at the 2-sided Fisher exact test with 5% significance	

Regeneron Pharmaceuticals, Inc.

CONFIDENTIAL

Page 25 of 118

the primary efficacy analysis. These subjects receive AR101 dose escalation per the original protocol's 24-week up-dosing schedule. The minimum significant difference with approximately 122 subjects is approximately 20.7% between placebo plus AR101 and dupilumab plus AR101 assuming the placebo plus AR101 treatment effect is 40% at the 2-sided Fisher exact test with 5% significance level.

Efficacy Analysis Set

The full analysis set (FAS) includes all randomized subjects. Efficacy analyses will be based on the treatment allocated at randomization (as randomized).

The modified full analysis set (mFAS) includes all FAS subjects who undergo the post up-dosing DBPCFC at week 28 (visit 16 with a window of -7/+30 days) or discontinue from study prior to week 28 (visit 16 with a window of -7/+30 days).

The mFAS will be used for primary analysis for all efficacy endpoints. Analysis of the FAS will also be done for supportive analyses.

Safety Analysis Set

The safety analysis set (SAF) includes all randomized subjects who received any study drug; it is based on the treatment received (as treated). Treatment compliance/administration and all clinical safety variables will be analyzed using the SAF.

Primary Efficacy Analysis

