11.3. Analysis Sets

11.3.1. Efficacy Analysis Sets

The full analysis set (FAS) includes all randomized subjects. Efficacy analyses will be based on the treatment allocated at randomization (as randomized).

The modified full analysis set (mFAS) includes all FAS subjects who undergo the post up-dosing DBPCFC at week 28 (visit 16 with a window of -7/+30 days) or discontinue from study prior to week 28 (visit 16 with a window of -7/+30 days).

The mFAS will be used for primary analysis for all efficacy endpoints. Analysis of the FAS will also be done for supportive analyses.

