11.4.3.1. Primary Efficacy Analysis

The primary endpoint will be analyzed using the Cochran-Mantel-Haenszel test adjusted by randomization stratification factors to assess the treatment difference in the proportion of responders (ie, those who "pass" a post up-dosing DBPCFC with 2044 mg [cumulative] peanut protein at visit 16 [week 28 with a visit window of -7/+30 days]) in the mFAS. Estimate of treatment difference, p-value, and the 2-sided 95 % confidence interval will be provided.

In addition, the primary efficacy endpoint will be performed on the FAS as a supportive analysis.

If a subject does not have available post up-dosing DBPCFC data at visit 16, the subject will be considered as a non-responder regardless of reasons for missing data.

Sensitivity analyses will include an analysis of the subset of subjects with available post up-dosing DBPCFC data from visit 16.

Subgroup analysis (eg, by baseline weight group) will also be performed.

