2.3. Sample Size and Power Considerations

It is assumed that the proportion of subjects who achieve a cumulative dose of 2044 mg of peanut protein during a post up-dosing DBPCFC at visit 16 in placebo plus AR101 arm will be 40%, based on an Aimmune presentation at the 2018 American Academy of Allergy, Asthma & Immunology–World Allergy Organization Joint Congress; with the proportion of subjects in dupilumab plus AR101 arm assumed to be 65%, which is considered to be clinical meaningful benefit by adding on dupilumab treatment. A sample size of approximately 156 subjects (104 in dupilumab plus AR101 and 52 in placebo plus AR101) will have 80% power to detect the treatment difference of 25% between placebo plus AR101 and dupilumab plus AR101 at the 2-sided 5% significance level (the minimum significant difference is approximately 17.8%). The sample size calculations were done by Fisher exact test using nQuery (7.0).

[figure not shown]
Approximately 122 subjects who undergo the post up-dosing DBPCFC at Week 28 (visit 16 with a window of -7/+30 days) as per protocol or discontinue from study prior to Week 28 (visit 16 with a window of -7/+30 days) will be included in the primary efficacy analysis. These subjects receive AR101 dose escalation per the original protocol's 24-week up-dosing schedule. The minimum significant difference with approximately 122 subjects is approximately 20.7% between placebo plus AR101 and dupilumab plus AR101 assuming placebo plus AR101 treatment effect is 40% at the 2-sided Fisher exact test with 5% significance level.

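### The 80% power is stated for 156 subjects, but the primary analysis uses about 122, where power is about 70–75% at an assumed 2:1 split and is not stated

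*Protocol*

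**What the plan says.** Protocol 11.2 assumes that the pass rate "in the placebo plus AR101 arm will be 40"% and that the dupilumab arm reaches 65%. With 104 and 52 subjects the trial "will have 80% power to detect the treatment difference of 25% between placebo plus AR101 and dupilumab plus AR101". The calculation used Fisher's exact test, and Protocol 11.1 sets the level: the hypothesis "will be tested at the 5% 2-sided significance level". SAP 2.3 repeats the claim: "A sample size of approximately 156 subjects (104 in dupilumab plus AR101 and 52 in placebo plus AR101) will have 80% power". The synopsis carries it too.

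The next paragraph of Protocol 11.2 changes the number analysed. "Approximately 122 subjects who undergo the post up-dosing DBPCFC at week 28", or who leave the study before then, make up the primary efficacy analysis. Protocol 11.3.1 confirms this: "The mFAS will be used for primary analysis for all efficacy endpoints". The full analysis set (FAS) of all randomized subjects becomes supportive. For the smaller set, Protocol 11.2, the synopsis and SAP 2.3 report only that the minimum "significant difference with approximately 122 subjects is approximately 20.7"%.

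The planned test also differs from the one used for sizing. Protocol 11.4.3.1 says: "The primary endpoint will be analyzed using the Cochran-Mantel-Haenszel test adjusted by randomization stratification factors".

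**The concern.** The only power figure in either document belongs to the supportive analysis. For 156 subjects the plan gives both a power and a minimum significant difference. For the set that decides the trial it gives only the second. A reader can easily carry the 80% across to the primary test, where it does not apply.

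The minimum significant difference answers another question. It is the smallest observed difference that reaches p ≤ 0.05, and it does not say how often a true 25-point effect would be detected.

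This bears on how a non-significant primary result would be read. The 25-point effect is the one the plan itself calls clinically meaningful. Under the hierarchical procedure (Protocol 11.4.3.3, SAP 5.6.3), a missed primary also blocks inference on the first secondary endpoint.

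**Working it through.** **Inputs**
- Pass rates 40% (placebo plus AR101) and 65% (dupilumab plus AR101), sizing by Fisher's exact test, N = 156 (104:52) and about 122: Protocol 11.2.
- Two-sided 5% level: Protocol 11.1.
- Randomization 2:1: Protocol 8.5.
- The split of the 122 is not given. I assume about 2:1, that is 81:41, with 82:40 and 80:42 as neighbours.

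**Step 1. Reproduce the plan's figures.** Fisher power is the sum of the two binomial probabilities over every outcome table with two-sided p ≤ 0.05. At 104:52 it is 81.1%, so the stated 80% holds for 156.

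For the minimum significant difference with 122, take the placebo count nearest 40% and find the smallest significant dupilumab count:
- 81:41: 48/81 − 16/41 = 59.3% − 39.0% = 20.2 points
- 82:40: 50/82 − 16/40 = 61.0% − 40.0% = 21.0 points
- 80:42: 49/80 − 17/42 = 61.3% − 40.5% = 20.8 points

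These bracket the stated 20.7. They are consistent with a split near 2:1 but do not prove one. The same method at 104:52 gives 61/104 − 21/52 = 18.3 points, against the stated 17.8.

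**Step 2. Power at 122 by the uncorrected z formula.**

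Power = Φ[(d − 1.96·SE₀)/SE₁], where SE₀ = √(p̄(1−p̄)(1/n₁+1/n₂)) and SE₁ = √(p₁(1−p₁)/n₁ + p₂(1−p₂)/n₂).

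- 104:52: p̄ = (67.6 + 20.8)/156 = 0.5667, SE₀ = 0.0842, SE₁ = 0.0825. Then z = (0.25 − 0.1650)/0.0825 = 1.03, and power is 84.9%.
- 81:41: p̄ = (52.65 + 16.4)/122 = 0.5660, SE₀ = 0.0950, SE₁ = 0.0931. Then z = (0.25 − 0.1862)/0.0931 = 0.686, and power is 75.4%.

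**Step 3. All methods side by side.**

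| Split | Fisher | z formula | CMH (simulated) |
|---|---|---|---|
| 104:52 | 81.1% | 84.9% | 84–85% |
| 81:41 | 72.2% | 75.4% | 73–75% |
| 82:40 | 70.7% | 74.9% | 73–74% |
| 80:42 | 70.4% | 75.8% | 74–75% |

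The CMH column uses 100,000 simulated trials per setting over the 2 × 3 randomization strata, without continuity correction. The stratum mix is assumed: IgE 50:50 or 65:35, and weight equal thirds or 35/50/15. Pass rates are either equal across strata or 15 points apart by IgE level, with the overall 65% and 40% held fixed.

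**Step 4. What the 20.7% implies.** If the true rates were 60.7% and 40%, power at 81:41 would be 53.7% by Fisher and 58.3% by the z formula.

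**Step 5. True difference needed for 80% power at 81:41, placebo rate 40%.** 27.2 points by Fisher, 26.4 points by the z formula.

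**The case against.** Nothing in the sample size text is numerically false. The 80% names its own denominator, and the move to 122 is disclosed together with the rise in the minimum significant difference from 17.8% to 20.7%. The smaller set follows from pandemic changes to up-dosing rather than a new sizing decision. A non-significant result would in any case be read from its estimate and 95% confidence interval, which the plan provides. All of this is fair, and it is why the point concerns reporting and does not challenge the design. It does not supply the missing figure: a section that justifies the sample size should give the power of the analysis it supports.

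The second objection is that the replacement figure is uncertain. The mFAS is selected on events after randomization, so 2:1 may not hold. Fisher gives 70.6% at 86:36 and 75.4% at 74:48. At the more extreme splits of 90:32 and 70:52 it gives 65.4% and 77.3%. At 81:41 the method alone moves the answer from 68.7% (Fisher with doubled tail) to 76.2% (exact power of the uncorrected chi-square test). The CMH simulation leaves out the multiple imputation that SAP 5.6.1 plans for COVID-19 missingness. SAP 3.1 also leaves early discontinuers out of its mFAS definition, while Protocol 11.3.1 includes them, so the final number may not be 122. These points call for stating the split and the test beside the figure. None of the splits and methods above brings the power for 122 to 80%.

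**Conclusion.** The concern holds. The 80% is right for 156 subjects but is not the power of the primary analysis, and no power for that analysis is stated. For 65% against 40% at the two-sided 5% level, with 122 subjects split about 2:1, power is about 70–75% (69–76% across all the methods tried). The loss is roughly 8 to 11 points under any one test. The chance of missing the planned effect rises from about 15–19% to about 25–30%. This assumes that the 2:1 ratio and the planned pass rates carry over to the mFAS, and that about 122 is the number analysed. The design is not invalidated.

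**What to change.** In Protocol 11.2, the synopsis and SAP 2.3:
- State that the primary mFAS of about 122 has about 70–75% power for 65% against 40%, and name the assumed split (2:1) and the test. Alternatively, state that 80% power at this size needs a true difference of about 26–27 points.
- Label the 80% as applying to the supportive FAS of 156.
- Align the mFAS definitions in Protocol 11.3.1 and SAP 3.1 at the same time, so that the power statement refers to one set.

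For the power statement the cost is text only: a published figure becomes less favourable, and the test, alpha level, primary analysis set and number of subjects stay as they are.
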